Other theories on the mechanism of BFR on tissue healing involves the acute inflammatory response during blood flow restriction. IL-6 is a cytokine released after exercise in response to muscle microdamage, and plays a role in skeletal muscle regeneration by recruitment of inflammatory cells.³⁴ As with IGF-1, IL-6 also contributes to the activation and proliferation of satellite cells, as well as activating the mTORC-1 pathway.^{35, 36} It is important to note, however, that while the studies above have been performed in the setting of BFR use on healthy individuals, the mechanism of action in injured patients has not been evaluated. Furthermore, these studies have only measured blood markers prior to BFR cuff placement and immediately after, with none evaluating the trend in changes of markers over multiple sessions of BFR therapy.

Objectives

Aim 1: To determine whether patients with non-surgical rotator cuff and biceps tendinopathy undergoing BFR rehabilitation show increased improvements in shoulder function relative to patients undergoing routine therapy with a tourniquet that is not occluding arterial blood (i.e. sham BFR). We hypothesize that patients undergoing rehabilitation with BFR tourniquet pressurized to recommended therapeutic specifications will have increased muscle strength and CSA, as well as higher functional score averages compared to patients undergoing rehabilitation with sham BFR. We will be measuring shoulder strength in injured and non-injured arms for both study groups using a Biodex testing machine. Ultrasound will be used to measure the CSA of the rotator cuff muscles. Both strength testing and ultrasound measurements will be performed before and after the rehabilitation protocol has been completed. Patients will receive questionnaires evaluating shoulder function at baseline, once cleared by physical therapy, as well as 6 and 12 months after completing rehabilitation.

Aim 2: To determine whether trends in blood biomarker concentration differ between both groups throughout the rehabilitation protocol. We hypothesize that patients undergoing BFR will have higher

Protocol version:

Template updated 9.24.14

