Patients assigned to the BFR group will undergo BFR therapy during each session throughout the entire rehabilitation protocol. The standard rehabilitation protocol recommended by the physical therapists at WFBH is 2 sessions a week for 6 weeks. The therapy will be performed by one of the WFBH physical therapists who is trained and certified in using BFR therapy. The standard BFR protocol that is implemented by the Wake Forest physical therapists and recommended by expert opinion involve performing 4 separate exercises during each session. Each exercise will be done 4 consecutive times, starting with 30 repetitions, followed by 15 repetitions performed 3 times. Each set will be separated by 30 seconds break. After the finishing the 4 sets for one specific exercise, the patient will rest for 2 minutes prior to beginning the next 4 sets. In summary, the patient will perform 4 sets of 4 different exercises, perming the following repetitions: 30-15-15-15.

In the BFR group, the tourniquet will be pressurized to 50% limb occlusion pressure (LOP), which is the pressure necessary for occluding 50% of arterial limb flow in the upper extremity. The amount of cuff inflation is personalized to each patient as a safety measure and for maximizing the acute physiological response.⁴⁰ In the sham BFR group, the tourniquet will be pressurized to 0% occlusion pressure, while maintaining enough pressure to keep the tourniquet in place.

Protocol version:

Template updated 9.24.14

The tourniquet system (Delfi, Medial Innovations Inc) used in our physical rehabilitation clinic allows a patient specific LOP to be measured and automatically calculates the patient's personalized tourniquet pressure (PTP) as percentage of LOP. As an additional safety measure, the cuff automatically shuts off after 8 minutes to prevent prolonged restriction, and is locked from turning back on for 2 minutes. The sets for each exercise are structured so that the patient is able to finish 4 sets of one specific exercise within the 8 minute time limit.

Shoulder Strength and Cross Sectional Area Measurement

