Isocentric shoulder strength will be measured for injured and non-injured arms for both groups at baseline, half-way through the strength training phase of rehabilitation, and once rehabilitation has completed. A biomed testing machine will be used to evaluate changes in strength over time. Shoulder strength measurements will include shoulder flexion, abduction, external rotation, and internal rotation, as well as elbow flexion. Strength testing will be performed prior to beginning the rehabilitation session. Each test will be performed 3 times and the measurement will be averaged.

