Ultrasound will be used to quantify the changes in rotator cuff muscle before and after therapy. As previously described, the supraspinatus and infraspinatus muscles will be measured in each patient using a standard technique.²⁷ A multifrequency linear transducer (5-15 MHz) on a GE Logic S7 Expert will be used throughout the study. In order to measure the supraspinatus, the patient will sit in a chair, with the examiner standing behind the patient. The muscle belly of the supraspinatus and infraspinatus muscles will be evaluated while the patient had their hand placed on the anterior ipsilateral thigh for the examination. The muscle bellies of the supraspinatus and infraspinatus will be measured in the perpendicular plane to the long axis of their central tendon and muscle bellies to measure their respective cross sectional area and circumference. Landmark for obtaining measurement of the supraspinatus will be obtained by palpating the posterior corner of the acromion and measuring 8 cm medially along the spine of the scapula. From this position the transducer will be placed in the plane perpendicular to the spine of the scapula to visualize the cross section of the supraspinatus muscle belly and its central tendon. Landmark for obtaining measurement of the infraspinatus will be obtained by palpating the posterior corner of the acromion and measuring 5 cm medially along the spine of the scapula. From this position the transducer will be placed in the plane perpendicular to the spine of the scapula to visualize the cross section of the infraspinatus muscle belly and central tendon. Because the footprint of the transducer is smaller than the width of the muscle belly, panoramic images acquisition will be accomplished using LOGICView mode. The panoramic glide will be stopped once the full myofascial border between the infraspinatus and teres minor were in view. The difference between pre- and post-therapy cross sectional area of each muscle will be compared between both BFR and sham BFR groups.

Blood Biomarkers

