Blood samples will be acquired at baseline prior to intervention and at specific time points throughout the rehabilitation process to evaluate the effect of BFR therapy on the recovery of muscle, tendon, and ligamentous damage. Samples will be collected prior to beginning physical therapy, half-way through the structured protocol, and once the patient has completed rehabilitation. These blood samples will be collected by a member of the research team, who is trained in phlebotomy and is someone other than the principal investigator, and stored in a locked freezer until all samples for all patients have been collected. The patients will receive the blood draws in the physical therapy clinic on the day of their rehabilitation appointment. Once completed, GH, IGF-1, and IL-6 will be quantified using ELISA assays performed in the Wake Forest orthopedic surgery department. Each sample will have 3 technical duplicates analyzed to avoid loss of data during sample processing.

Patient Functional Status

Protocol version:

Template updated 9.24.14

Shoulder/Elbow functional status will be assessed using the following questionnaires that have been previously vetted for evaluation after upper extremity surgery: *Quick Disabilities of the Arm, Shoulder, and Hand (DASH)* survey, American Shoulder and Elbow Surgeons (ASES) standardized assessment form, visual analog scale for pain and satisfaction, and return to sport/daily activity questionnaires.^{42, 43} Patient reported outcomes will be captured prospectively over the course of one year using the PatientIQ, a web-based data collection healthcare platform. A blinded de-identified email and/or text message will be sent at baseline, and once cleared by therapy, as well as 6 and 12 months after completing therapy. After three days, if a participant does not respond to the survey, a second email and/or text message will be sent. If the participant does not respond after three consecutive weeks, a phone call will be administered to encourage continued participation.⁴⁴

Outcome Measure(s)

- *Shoulder strength, and rotator cuff muscle cross sectional area,*
- *Blood markers: GH, IGF-1, and IL-6*
- *Patient reported outcome measures: DASH, ASES, visual analog scale for pain and satisfaction*

Analytical Plan

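### The protocol specifies no masking to arm or visit for those who acquire or measure the ultrasound CSA images or run the strength test, although the control is a sham cuff

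*Combined protocol and SAP*

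**What the plan says.** Aim 1 (Objectives) hypothesises that BFR patients "will have increased muscle strength and CSA, as well as higher functional score averages compared to patients undergoing rehabilitation with sham BFR". The control is described under BFR Protocol: "In the sham BFR group, the tourniquet will be pressurized to 0% occlusion pressure, while maintaining enough pressure to keep the tourniquet in place".

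The section Shoulder Strength and Cross Sectional Area Measurement covers both physical outcomes.

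- **Strength** is measured by machine at baseline, half-way and at the end. On procedure it says "Each test will be performed 3 times and the measurement will be averaged", and on timing "Strength testing will be performed prior to beginning the rehabilitation session". It names no tester and gives no instruction script.
- **CSA** is measured before and after therapy. For the supraspinatus, "the patient will sit in a chair, with the examiner standing behind the patient". The transducer is placed from palpated landmarks, at 8 cm for the supraspinatus and 5 cm for the infraspinatus. For the panoramic view, "The panoramic glide will be stopped once the full myofascial border between the infraspinatus and teres minor were in view". The comparison is then: "The difference between pre- and post-therapy cross sectional area of each muscle will be compared between both BFR and sham BFR groups".

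In the protocol body, blinding is mentioned once, under Patient Functional Status, for the survey message: "A blinded de-identified email and/or text message will be sent at baseline". The only other occurrence is in the title of a cited trial in the reference list. The one rule separating staff roles, under Blood Biomarkers, covers phlebotomy and excludes only the principal investigator.

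**The concern.** A sham cuff can reduce differences in what patients expect. It does nothing about an examiner, reader or tester who knows the arm. Both physical outcomes leave that person some influence. For CSA, someone palpates the landmark, places the transducer by hand, ends the glide and obtains an area from the image. For strength, the patient's effort can respond to how the test is coached.

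Visit matters as well as arm. CSA is analysed as a pre-to-post change, so a reader who knows which image is the later one, and from which arm, could shift the change without intending to. The comparison of group averages in the Analytical Plan is an independent t-test, which cannot separate such a shift from a treatment effect. At stake is whether a difference in strength or CSA can be credited to BFR, and whether this pilot's effect estimates are safe to carry into a later trial.

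**Working it through.** **Step 1: is masking specified anywhere?** These are the places where it could be stated.

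| Section | What it gives | Masking of examiner, reader or tester |
|---|---|---|
| Objectives, Aim 1 | Sham control; expected direction | None |
| Study Arms | Randomisation by Excel | None |
| BFR Protocol | Cuff at 50% of limb occlusion pressure or 0%; therapy by a trained therapist | None |
| Strength and CSA measurement | Positions, landmarks, device, three trials | None; no person identified |
| Blood Biomarkers | Phlebotomist is not the principal investigator | Not about these outcomes |
| Patient Functional Status | Survey message | Not about these outcomes |
| Analytical Plan | t-test, chi-square, repeated measures ANOVA | None |
| Confidentiality and Privacy | Study identifier on data forms | Serves confidentiality; does not hide arm or visit from an assessor |

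Figure 1 and the consent form cannot be seen. The measurement text, where masking would normally be written, is present and silent.

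**Step 2: the plan's own figure.** The only power calculation concerns growth hormone: effect size 2.203, 6 per group, 90% power. With a two-sided 5% t-test (assumed), the noncentrality is 2.203 × √(n/2).

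- n = 5: 2.203 × √2.5 = 3.48, power 86.1%.
- n = 6: 2.203 × √3 = 3.82, power 92.9%.

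So 6 is the smallest group size that reaches 90%, and the figure reproduces. It has no bearing on assessor bias in CSA or strength.

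**Step 3: what a bias would do, as an illustration.** Inputs:

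- From the Sample Size text: a minimum of 8 and a hoped-for 12 per arm.
- From the Analytical Plan: an independent t-test.
- Assumed, because the documents do not give them: alpha 5%, two-sided, and a between-arm bias of b SD of the change score.

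With no true effect, the test statistic follows a noncentral t with df = 2n − 2 and noncentrality b × √(n/2). The false-positive rate is the probability that |t| exceeds the 97.5% point of the central t.

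- n = 8: df = 14, critical value 2.145, √(8/2) = 2.
- n = 12: df = 22, critical value 2.074, √(12/2) = 2.449.

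| Assumed bias b (SD) | Noncentrality, n = 8 | False positives, n = 8 | Noncentrality, n = 12 | False positives, n = 12 |
|---|---|---|---|---|
| 0 | 0 | 5.0% | 0 | 5.0% |
| 0.2 | 0.40 | 6.6% | 0.49 | 7.6% |
| 0.3 | 0.60 | 8.7% | 0.73 | 10.8% |
| 0.5 | 1.00 | 15.4% | 1.22 | 21.6% |

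For the same bias, the rate is higher at 12 than at 8 per arm. Recruiting to the higher target does not dilute a systematic error.

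**The case against.** The strongest reply is that the plan already restricts assessor discretion. Landmarks are fixed in centimetres, the imaging plane and the machine are specified, the glide ends at an anatomical border, and strength is read from a machine and averaged over three trials. This stands as mitigation. But averaging reduces random error only, and a stopping rule still has to be applied by a person who may know the arm.

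The second reply is that silence is not evidence of bias. This also stands, and it rules out several stronger readings that a reader might infer:

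- *That assessors know the arm.* The documents do not say so; they do not identify the assessors.
- *That staff who set the cuff run the strength test, in the therapy clinic.* The protocol gives the timing of the test, not its place or tester. The clinic location is stated for blood draws.
- *That a reader hand-traces the muscle border.* No measurement method for the saved or live image is described.
- *That images are already stored, so blinded reading costs nothing.* Storage is stated for blood samples only.
- *That patients are effectively masked by the sham, or that its benefit is largely lost.* Neither is stated or shown. Matched cuff contact may still help with effort and questionnaires.

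Third, the false-positive rates rest on an assumed bias, so they are not evidence about this trial. That is correct, and they are offered only to show scale.

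Finally, this is a pilot. It nevertheless tests directional hypotheses between arms, so the point still applies.

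**Conclusion.** The concern holds as an omission. The protocol does not specify masking to arm or visit for the person who acquires or measures the CSA images or who runs the strength test. Followed as written, it leaves two sham-controlled Aim 1 outcomes open to detection bias.

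Bias is possible, not demonstrated, and neither its size nor its direction can be taken from the documents; a direction favouring BFR is plausible only because that is the stated hypothesis. Under the assumptions above, a bias of 0.2 to 0.5 SD would move a nominal 5% error rate to between 6.6% and 15.4% at 8 per arm, and between 7.6% and 21.6% at 12 per arm. This should be corrected because the main remedy is cheap. It does not by itself invalidate the design.

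**What to change.** In the section Shoulder Strength and Cross Sectional Area Measurement:

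1. **CSA reading.** State that every panoramic image is saved under a random code, and that CSA is measured off-line in one batch by an existing team member with arm and visit (pre or post) hidden. This is the main change.
2. **Strength test.** Add a fixed instruction script, used identically for every patient and visit.
3. **Staffing, where it allows.** State that the therapist who delivers a patient's cuff sessions does not scan or strength-test that patient. This may need another person, so it should not be a condition for the first two changes.
4. **Remaining limit.** Say openly that off-line reading does not mask image acquisition, so bias from transducer placement or the glide is not excluded.

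The cost is saving and coding the images and one batch reading by current staff. CSA results will not be available in real time. Sample size, visits and treatment are unchanged.

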- Based on the literature review, there are no published studies that have evaluated the effect BFR therapy on shoulder injury rehabilitation. Some studies have taken a pilot study approach and used 12 patients in each limb based off what has been recommended in the previous literature.^{45, 46} However, others evaluating the effect of BFR therapy on quadriceps strength after ACL reconstruction have evaluated their sample size based on their own preliminary pilot studies and established sample sizes of 24 per group in order to achieve 80% power.⁴⁷ A previous study comparing GH levels between healthy individuals undergoing BFR strength training vs those without was used to estimate the number of patients needed to achieve at least 80% power.⁴⁸ Based on the difference in GH between the two groups, an effect size of 2.203 was calculated. An *a priori* power analysis demonstrated that 6 patients were required in each group in order to achieve a power of 90%. However, we feel that the standard deviation of the current study may be larger, and as such, for this pilot study we will recruit a minimum of 8 patients in each arm. However, we hope to recruit at least 12 in each arm by the time the study is completed in order to have 24 patients similar to established sample sizes in other BFR studies.⁴⁷

Interventions and Interactions

Study Arms

Once consented, patient will be enrolled in of the two study arms prior to beginning physical rehabilitation. Patients will be randomized to one of the study arms using Microsoft Excel (version

Protocol version:

Template updated 9.24.14

16.82). Prior to beginning therapy, patients will undergo a blood draw at the clinic to establish baseline blood biomarkers. The patient will also undergo upper extremity physical strength assessment, and functional evaluation prior to beginning therapy. Baseline patient reported functional status will also be evaluated through upper extremity-specific questionnaires. During physical therapy, participants will undergo blood draws, receive electronic questionnaires, and undergo assessment of biomechanical at specified time points outlined below. Patient questionnaire information will be de-identified and coded into an encrypted centralized database. The schematic in **figure 1** provides the time points of each datapoint collected.

[figure not shown]

Figure 1. Schematic of study workflow indicating timepoints for carrying out study aims

BFR Protocol

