Subject descriptive statistics will be analyzed using mean \pm standard deviation for continuous variables, and frequencies and percentages for categorical variables. Normality analyses will be performed utilizing data visual inspection and parametric testing. Averages between the two groups will be compared using independent T-test and chi-square analysis were appropriate. Repeated measures ANOVA will be performed to evaluate statistical significance in blood biomarkers.

Human Subjects Protection

Subject Recruitment Methods

Describe how and where subjects will be identified and recruited. Indicate who will do the recruiting, and tell how subjects will be contacted. Describe efforts to ensure equal access to participation among women and minorities. Describe how you will protect the privacy of potential subjects during recruitment.

- For studies using recruitment flyers and advertisements, please provide copies of these materials for IRB review.
- For studies using PHI to identify subjects via medical records search or referral from a treating physician, who will then be contacted, you will need a limited waiver of HIPAA authorization, If this applies to your study, please provide the following information:
 - Under this limited waiver, you are allowed to access and use only the minimum amount of PHI necessary to review eligibility criteria and contact potential subjects. What information are you planning to collect for this purpose?
 - How will confidentiality/privacy be protected prior to ascertaining desire to participate?
 - When and how will you destroy the contact information if an individual declines participation?

Protocol version:

Template updated 9.24.14

Informed Consent

Signed informed consent will be obtained from each subject. Informed consent will be gathered by the one of the study coordinators or study investigators in clinic after being screened with inclusion/exclusion criteria and prior to undergoing non-surgical treatment for the injury.

Confidentiality and Privacy

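### Aim 1 outcomes are compared without adjustment for the baseline values the trial collects, which gives up some precision at 8 to 12 patients per arm

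*Combined protocol and SAP*

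**What the plan says.** The Analytical Plan says: "Averages between the two groups will be compared using independent T-test and chi-square analysis were appropriate". It reserves repeated measures ANOVA for the blood biomarkers. It does not tie the t-test to named outcomes, but it offers no other between-group test for a continuous measure, so by elimination the t-test covers strength, CSA and questionnaire scores.

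A baseline value exists for each of these:

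- **Strength and CSA.** Aim 1 in the Objectives says "Both strength testing and ultrasound measurements will be performed before and after the rehabilitation protocol has been completed". The section on strength and CSA measurement adds "Isocentric shoulder strength will be measured for injured and non-injured arms for both groups at baseline", with further strength tests midway and at the end.
- **Questionnaires.** Under Patient Functional Status, the survey message "will be sent at baseline, and once cleared by therapy, as well as 6 and 12 months after completing therapy".

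The quantity to be compared is clear only for CSA: "The difference between pre- and post-therapy cross sectional area of each muscle will be compared between both BFR and sham BFR groups". For strength the text points to change: "A biomed testing machine will be used to evaluate changes in strength over time". For questionnaires the Aim 1 hypothesis speaks of "higher functional score averages compared to patients undergoing rehabilitation with sham BFR", which reads as a final value, but the aim itself is framed as greater improvement in function, which reads as change.

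On size, the Sample Size section says "for this pilot study we will recruit a minimum of 8 patients in each arm", and hopes for at least 12.

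**The concern.** A t-test on final values ignores baseline. A t-test on change subtracts baseline with its slope fixed at 1. ANCOVA estimates that slope from data already in hand. With 16 to 24 patients the interval around each arm difference will be wide, and in a pilot that interval is a main product. If the fixed slope of 0 or 1 is far from the true one, the planned test gives a wider interval than the same data could support. Because the plan leaves final value or change open for strength and questionnaires, that choice could also be made after the data are seen.

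**Working it through.** **The plan's own figure.** The Sample Size section gives 6 per group for 90% power at a growth hormone effect of 2.203 SD. With a two-sided 5% t-test (alpha is not stated; this is assumed), power is 86.1% with 5 per group and 92.9% with 6, so 6 reproduces. That figure concerns growth hormone, does not depend on baseline adjustment, and gives no power for any Aim 1 outcome.

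**Inputs.** From the documents: n = 8 or 12 per arm. Assumed: baseline to follow-up correlation r (shown over a range), a true difference d = 1 SD, normal data, equal SDs at baseline and follow-up, two-sided 5%, no dropout.

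**Variance of the arm difference, in follow-up SD units squared (N = 2n).**

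- Final value: 2/n
- Change score: 2(1 − r) × 2/n
- ANCOVA, on average: (1 − r²) × (1 + 1/(N − 4)) × 2/n. The middle factor is the price of estimating the slope: 1 + 1/12 = 1.083 at 8 per arm and 1 + 1/20 = 1.05 at 12.

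Example, 8 per arm, relative to final value:

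- r = 0.5: change 2 × 0.5 = 1.00; ANCOVA 0.75 × 1.083 = 0.81.
- r = 0.7: change 2 × 0.3 = 0.60; ANCOVA 0.51 × 1.083 = 0.55.

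**Power.** Noncentral t with noncentrality d/√variance, on 2n − 2 df for the two t-tests. For ANCOVA, 2n − 3 df, with variance (1 − r²)(2/n)(1 + F/(2n − 2)) averaged over F on 1 and 2n − 2 df. For the final value at 8 per arm, noncentrality is 1/√0.25 = 2.0 on 14 df, giving 46%.

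| n per arm | r | Final value | Change | ANCOVA |
|---|---|---|---|---|
| 8 | 0.3 | 46% | 35% | 47% |
| 8 | 0.5 | 46% | 46% | 54% |
| 8 | 0.7 | 46% | 67% | 70% |
| 8 | 0.8 | 46% | 84% | 84% |
| 12 | 0.3 | 65% | 51% | 67% |
| 12 | 0.5 | 65% | 65% | 75% |
| 12 | 0.7 | 65% | 86% | 89% |
| 12 | 0.8 | 65% | 96% | 97% |

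**Mean 95% CI half-width, in SD (needs no effect size).** Final value/change/ANCOVA:

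- 8 per arm: 1.05/1.05/0.95 at r = 0.5; 1.05/0.82/0.79 at r = 0.7; 1.05/0.67/0.66 at r = 0.8.
- 12 per arm: 0.84/0.84/0.74; 0.84/0.65/0.61; 0.84/0.53/0.52.

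**Where the gain ends.**

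- Against final value, variances are equal when (1 − r²) × 1.083 = 1, r ≈ 0.28 at 8 per arm, and at r ≈ 0.22 with 12. Below that ANCOVA costs a little: 44.6% against 46.1% at r = 0.2 with 8 per arm, and about 3 points at r = 0.
- Against change, variances are equal when (1 + r) × 1.083 = 2, r ≈ 0.85 at 8 per arm, and at r ≈ 0.90 with 12. At r = 0.9 with 8 per arm, power is 98.1% for ANCOVA and 98.6% for change.

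**Unequal SDs.** If the baseline SD is k times the follow-up SD, the change-score variance factor becomes 1 + k² − 2rk. At r = 0.7 and 8 per arm, ANCOVA power stays at 70.4%:

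- k = 0.8: 1 + 0.64 − 1.12 = 0.52, change-score power 73.2%.
- k = 0.7: 1 + 0.49 − 0.98 = 0.51, change-score power 74.0%.
- k = 1.25: 1 + 1.5625 − 1.75 = 0.8125, change-score power 54.2%.

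**Check by simulation** (40,000 trials per setting): power agrees to within about 1 point, and type I error is about 5% for all three tests.

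**The case against.** The best reply is that nothing is broken. With randomised arms all three tests are valid, and this is a pilot. That stands: the point is an improvement, not the correction of an error. A reader might infer that the unadjusted t-test biases the comparison; the documents give no ground for that.

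The second reply concerns the comparator. Final-value tests look worst at high r, and a reader might take that gap as the trial's loss. The documents do not support this. CSA is explicitly a pre-post difference, strength is described as change, and the aim for function is worded as improvement. Against change scores the gain is material only at r of about 0.5 or less. For CSA over a six-week programme r may well be high, and the planned difference would then already capture nearly all of the benefit.

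Third, a reader might infer that ANCOVA is always close to the best choice whatever r is. That holds only with equal SDs and r not near 0, and the unequal-SD figures show a reversal. No SD or r is given for any outcome, and bounded questionnaire scores at this sample size were not examined.

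What remains is that r is unknown, each unadjusted test fixes a slope in advance, and the adjustment needs no new data.

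**Conclusion.** The point holds as a modest, near-free gain in precision. Under the stated assumptions, ANCOVA adds about 8 to 10 points of power over change scores at r = 0.5, about 3 at r = 0.7 and under 1 at r = 0.8. It is slightly worse at r = 0.9 with 8 per arm, and about 3 to 4 points worse at r = 0.7 with 8 per arm if the baseline SD is 0.8 to 0.7 of the follow-up SD. Over final values it adds 8 to 10 points at r = 0.5 and 24 at r = 0.7, little or nothing at about 0.3 or below, and it costs up to about 3 points near r = 0 with 8 per arm.

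That baseline is collected and no covariate is named is firm. That the t-test applies to Aim 1 is an inference, and the size of the gain for any actual outcome is not established. The point does not extend to the blood biomarkers, which have their own repeated measures analysis.

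**What to change.** In the Analytical Plan, make the main between-group comparison of each continuous Aim 1 outcome (strength, CSA, questionnaire scores) an ANCOVA of the follow-up value on arm plus the same outcome's baseline value. Name in advance the follow-up visit for each outcome and, for strength, the limb measure analysed, since both arms of each patient are tested. Report the adjusted difference with its 95% CI. Keep the planned t-test, or for CSA the pre-post difference, as a sensitivity analysis.

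The cost is wording and one degree of freedom per comparison. No visits, measurements or patients are added.
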